4.2.4 Fluid Biomarker Efficacy Endpoints

The fluid biomarker efficacy endpoints are listed in [Table 2](#). The arrows indicate the behavior of each outcome. A flat arrow indicates that the outcome maintains its values; a downward arrow indicates the outcome decreases; and an upward arrow indicates the outcome increases. The arrow with a circle on top indicates uncertainty in the change of direction. All data processed using ELISA platform will **only** be used for analyses related to the solanezumab drug.

Table 2: Fluid Biomarker Information

Analyte	Platform	Drug arm (S/G/Both)	**Expected change in disease (No treatment)	Expected change with effective drug CDR 0 at baseline	**Expected change with effective drug CDR > 0 at baseline	Obs Run In (Y/N)
CSF Total Abeta42 (free+bound)	ELISA*	S	↓	↑	↑	N
CSF Total Abeta1-40 (free+bound)	ELISA*	S	↔	↑	↑	N
CSF free AB1-40	ELISA*	S	↔	↓	↓	N
CSF free AB1-42	ELISA*	S	↓	↓	↓	N
CSF AB1-40	Lumipulse	G***	↔	↑	↑	Y
CSF AB1-42	Lumipulse	G***	↓	↑	↑	Y
CSF Tau	Lumipulse	Both	↑	↓	↓	Y
CSF pTau181	Lumipulse	Both	↑	↓	↻	Y
plasma AB1-40	ELISA*	S	↔	↑	↑	N
plasma AB1-42	ELISA*	S	↓	↑	↑	N
CSF NFL	SIMOA	Both	↑	↓	↓	Y
Plasma NFL	SIMOA	Both	↑	↓	↓	Y

*ELISA is modified innotest designed to work in the presence or absence of solanezumab
 ** Many markers level off or change direction in late stage disease
 *** The Lumipulse measures of Abeta will only be measured in gant placebo samples due to blinding of active vs. placebo

4.2.5 Other Additional Analysis Endpoints

The following endpoints will be used for exploratory analyses unless designated as secondary in the drug-specific SAP appendix.

- [Redacted]
- Imaging biomarkers:
 - [Redacted]
 - [Redacted]
 - [Redacted]
 - Tau PET measures of neurofibrillary tangle (NFT) burden.
- Cognitive Tests:
 - Raven’s Progressive Matrices (Set A), higher scores indicate better performance.

- Groton Maze Learning Test: Immediate Recall, 30-min Delayed Recall, 30-min Reversed Recall. For all these tests, lower scores indicate better performance.
- [REDACTED]
- [REDACTED]
- Clinical Assessments:
 - Geriatric Depression Scale, higher scores indicate worse performance. Both the change from baseline and % of subjects whose score became larger than 4 during the trial will be modeled.

[REDACTED]

5 POWER ESTIMATION

The power analyses presented here are based on trial simulation of the primary DIAN multivariate cognitive endpoint (DIAN-MCE) and the use of the multivariate disease progression model (MDPM).

The primary analysis is a single hypothesis test using the MDPM with four clinical/cognitive tests being modeled simultaneously (vs. the previous primary analysis using univariate DPM models of the DIAN Cognitive Composite).

Power Estimation using the MDPM

The power estimate for each scenario is presented in [Appendix VI](#). MDPM with dynamic borrowing of the eligible DIAN-OBS subjects (see [Section 7.2](#) for more details about these eligible subjects and [Section 12.1.4](#) for more details about the dynamic borrowing) led to approximately 95.9% power for a 30% effect size.

6 SEQUENCE OF PLANNED ANALYSES

6.1 Interim Analyses

Study drug-specific biomarker interim analyses may be conducted for each study drug to determine target engagement; details about these interim analyses are presented in the drug-specific SAP appendices.

6.2 Final Analyses and Reporting

A blinded data review meeting will be held prior to unblinding for efficacy analysis for the double-blind portion for a study drug. Meeting Minutes will be produced after the meeting to document the items discussed in the meeting but not reflected in this SAP. Any additional clarifications identified in the blinded data review meeting which are to be included in the final analysis will be identified as pre-specified and included in the CSR.

Note that the clinical database will not be permanently locked at the time of unblinding for efficacy analysis but will be considered clean for all datapoints other than for items related to safety follow-up. An unblinding plan and the minutes for the data review meeting will document individuals who are to be either subject-unblinded or group-unblinded between the unblinding for efficacy analysis and the database lock. All outputs will be rerun after the database lock, with any changes to data that impact primary efficacy results being clearly identified in the CSR.

Results from selected post hoc exploratory analyses which are not identified in this SAP but are deemed relevant to support the planned trial analyses will be documented and reported in the CSR; these results will be clearly identified as post hoc.

7 ANALYSIS POPULATIONS

In accordance with recommendations given in guidelines E3 [3] and E9 [1] of the ICH, and Protocol Amendment 10 [2] of the trial, statistical analyses are planned for the populations of trial subjects described below. To precisely define the analysis populations, we pre-specify the definitions of the type of placebo/control groups and the primary endpoint.

7.1 Types of Placebo/Control Groups

DIAN-TU-001 is intended as a platform trial with multiple agents, two of which (gantenerumab and solanezumab) have enrolled concurrently and met the recruitment goal. Placebos from the different study arms of DIAN-TU-001 and controls from DIAN-OBS will constitute the analysis populations.

To illustrate the proposed approach for pooling the control group, the following definitions, which were developed to be applicable for an arbitrary treatment (named treatment A), are pre-specified (Figure 1).

[figure not shown]

Figure 1: Depiction of the pooled control group and its components. Because of the DIAN-OBS run-in subjects, the Direct and Concurrent placebo arms have some overlap with the Eligible DIAN-OBS group; but for conciseness, they are separated in this figure.

- **Direct Placebos:** the group of **mutation positive** subjects who were randomized to the blinded placebo for treatment A.
- **Concurrently Randomized Placebos:** the group of **mutation positive** subjects who were randomized to placebo while treatment A was actively randomizing, but were not direct placebos for A (i.e., they were direct placebos for treatment B).
- **Mutation positive placebos:** direct placebos + concurrently randomized placebos
- **Eligible DIAN-OBS Subjects:** the group of **mutation positive** subjects who enrolled in the DIAN-OBS study and met the eligibility criteria as described in [Section 7.2](#).
- **DIAN-OBS Run-in Subjects:** **Eligible DIAN-OBS Subjects** who also enrolled in the DIAN-TU-001 study.
- **DIAN-OBS Non-run-in Subjects:** **Eligible DIAN-OBS Subjects** who did not enroll in the DIAN-TU-001 study.
- **Pooled Control Group:** the control group that includes Direct Placebo subjects, Concurrently Randomized Placebo subjects, and the eligible DIAN-OBS subjects.

7.2 Identification of Eligible Subjects from the DIAN-OBS Study

Determination of the DIAN-OBS Eligibility Criteria

A list of inclusion/exclusion criteria from the DIAN-TU-001 protocol that can be identified from the DIAN-OBS database were selected to identify eligible DIAN-OBS subjects.

DIAN-OBS Eligibility Criteria

All the individual DIAN-TU-001 inclusion/exclusion criteria (Listed in Section 4 of the Protocol) that can be validated using information from DIAN-OBS database have been identified and are presented in Table 3. The inclusion/exclusion criteria in Section 4 of the Protocol that are not presented in Table 3 are the criteria that cannot be validated using information from DIAN-OBS, and thus will not be used for DIAN-OBS eligibility determination.

To improve the comparability between the subjects from the two studies, DIAN-OBS subjects meeting any of the exclusion criteria listed in Table 3 at baseline or any post-baseline visit will be disqualified from being eligible for the control group and none of their data will be used for the DIAN-TU-001 primary analysis.

Table 3: DIAN-TU-001 Exclusion Criteria Specified in Protocol Amendment 10 that Can Be Validated Using Information from the DIAN-OBS Database

DIAN-TU-001 Exclusion Criteria	Corresponding DIAN-OBS Available Information	DIAN-OBS Data Source	Variable Names in DIAN-OBS (the values to remove)
4.2.3	Subjects with recent health history of stroke, cerebral hemorrhage or transient ischemic attack.	UDS Form A5 Subject Health History (Item 2a/2b) UDS Form B2: HIS and CVD	CBSTROKE (1, 2) CBTIA (1) HACHINSKI (>4) MCH (5+)
4.2.4	Subjects with alcohol or drug dependence sufficient to meet DSM-IV criteria currently or within the past 1 year.	UDS Form A5 Subject Health History (Item 7a,7c)	ALCOHOL (1) ABUSX (≠4)

DIAN-TU-001 Exclusion Criteria	Corresponding DIAN-OBS Available Information	DIAN-OBS Data Source	Variable Names in DIAN-OBS (the values to remove)
4.2.6, 7, 8, 9, 10	Subjects with recent myocardial ischemic events, congestive heart failure or major cardiovascular procedures including angioplasty / endarterectomy/stent, cardiac bypass procedure, pacemaker	UDS Form A5 Subject Health History (Item 1a,1c,1d,1e,1f)	CVANGIO (1) CVBYPASS (1) CVCHF (1) CVHATT (1)
4.2.3, 11	Subjects with active atrial fibrillation or in treatment with anticoagulation	UDS Form A4 Subject Medications UDS Form A5 Subject Health History (Item 1b)	DRUGID (d00210 d00022) CVAFIB (1)
4.2.18	Subjects with abnormalities of thyroid function studies, clinically significant deficiency in B12 (recent diagnosis or in active treatment)	UDS Form A4 Subject Medications UDS Form A5 Subject Health History (Item 1d,1e)	DRUGID (d00241 d00413 d00278) B12DEF (1) THYROID (1)

The DIAN-OBS study subjects will be selected as potential controls for the DIAN-TU-001 analysis if they **first** meet the following selection criteria during at least one DIAN-OBS study visit:

1. Mutation positive and without Dutch mutation. The DIAN-TU-001 excluded subjects from families with the Dutch mutation, based on evidence of atypical patterns of PiB PET abnormalities as well as differences in the pattern of disease progression since Dutch mutation tends to cause cerebral amyloid angiopathy instead of AD. Therefore, for the use of DIAN-OBS data in DIAN-TU 001 analyses this same mutation is excluded.
2. CDR \leq 1.
3. EYO between -15 to 10, inclusive.
4. For subjects only enrolled in DIAN-OBS: Meet the DIAN-TU-001 inclusion/exclusion criteria in the protocol that can be validated using subjects' information collected for DIAN-OBS (Table 3). DIAN-OBS run-in subjects already met the DIAN-TU-001 inclusion/exclusion criteria and thus will not be subject to Table 3 selection.

The earliest visit at which the above criteria are met is defined as the baseline visit.

When subjects meet the selection criteria 1- 4 listed above, they will be referred to as the Eligible DIAN-OBS Subjects if they also:

- had at least **two** administrations of at least one of the four tests contributing to DIAN-MCE and were only enrolled in the DIAN-OBS study but not in DIAN-TU-001;

or

- had at least **one** administration in DIAN-OBS and at least **one pre-dose** administration and **one post-dose** administration in DIAN-TU-001 of at least one of the four tests contributing to DIAN-MCE. (This subset of subjects henceforth are referred to as the DIAN-OBS Run-in Subjects within the Eligible DIAN-OBS Subjects).

When subjects meet the criteria above (as per DIAN-OBS data freeze 14) to be included in the DIAN-TU-001 primary analysis, selected secondary, and selected sensitivity analyses, only their data from the point of eligibility and thereafter will be included.

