7.5 Modified Intent-to-Treat (mITT) Analysis Population for DIAN-TU-001 Subjects

The mITT analysis population includes all randomized subjects who receive any treatment post-randomization and have at least one assessment for any one of the four tests contributing to DIAN-MCE at baseline and at least one post-baseline assessment for the same test that is either during treatment or no later than 56 days post-treatment. Subjects in the mITT analysis population will be allocated into treatment arms "as randomized".

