8.4 Handling of Missing Values

The primary analysis uses all observed data. There is no preliminary step of imputation for missing data, and the results obtained in this way are consistent with the missing at random assumption for all missing data. The sensitivity analyses to evaluate the effect of the missing-at-random

assumption are provided in Section D of [12.1.6.7](#). If subjects remained in the trial following drug discontinuation, the endpoints collected after drug discontinuation (only for drug discontinuation described in Protocol Section 4.4.1) will not be included in the primary, secondary and sensitivity analyses.

The clinical/cognitive tests contributing to DIAN-MCE collected more than one visit or more than 56 days (i.e., two visit intervals) after drug discontinuation will not be included in the primary analysis or secondary analysis.

Similarly, the clinical/cognitive tests contributing to secondary endpoints collected more than one visit or more than 56 days (i.e., two visit intervals) after drug discontinuation will not be included in the analysis.

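### DIAN-OBS-only controls lose all their data if they meet a Table 3 exclusion at any later visit, a selection on the future that randomized and run-in subjects do not undergo

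*SAP*

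**What the plan says.** Section 7.2 of the SAP sets the rule for external controls: "DIAN-OBS subjects meeting any of the exclusion criteria listed in Table 3 at baseline or any post-baseline visit will be disqualified", and "none of their data will be used for the DIAN-TU-001 primary analysis". The reason given is "To improve the comparability between the subjects from the two studies". Table 3 covers stroke or TIA, alcohol or drug dependence, cardiac events and procedures, atrial fibrillation or anticoagulation, and thyroid or B12 abnormalities.

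The same section exempts one part of the DIAN-OBS group: "DIAN-OBS run-in subjects already met the DIAN-TU-001 inclusion/exclusion criteria and thus will not be subject to Table 3 selection". It also gives a time-zero rule, "The earliest visit at which the above criteria are met is defined as the baseline visit", after which data from that point onward are used.

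For trial subjects, Section 7.5 says: "The mITT analysis population includes all randomized subjects who receive any treatment post-randomization", subject to a baseline and a post-baseline assessment of the same test. On later discontinuation, Section 8.4 says that "the endpoints collected after drug discontinuation (only for drug discontinuation described in Protocol Section 4.4.1) will not be included" in the analyses. Sections 3.6 and 8.1 give a 56-day window for the same purpose. All of these cut later data; none removes earlier data.

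**The concern.** Eligibility for a control group should be settled by what is known at the control's time zero. Here a DIAN-OBS-only subject with several valid years of testing is deleted because of a condition recorded afterwards. A randomized subject with the same history stays in the primary analysis up to the event at least. The retained DIAN-OBS-only subjects are therefore those who stayed free of every Table 3 condition throughout observation, which the randomized subjects need not be. If each visit carries some chance of a new Table 3 entry, the probability of being kept falls with every further visit, so the rule also selects against long follow-up. Screening at entry serves the stated aim of comparability; screening on follow-up works against it.

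The stake is the primary comparison. Sections 12.1.3 and 12.1.4 make DIAN-OBS the reference arm and shrink the placebo progression parameter towards it. If the later conditions are related to cognitive decline, the selected DIAN-OBS decline differs from the decline of comparable unselected carriers, and part of that difference enters the estimated drug effect.

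**Working it through.** **1. Who is selected on later events**

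| Group | Removed entirely for a later Table 3 event? | Source in SAP |
|---|---|---|
| DIAN-OBS-only controls | Yes, all data | 7.2 |
| DIAN-OBS run-in subjects | No, exempt from Table 3 | 7.2, item 4 |
| Randomized subjects (mITT) | No; discontinuation cuts later data only | 3.6, 7.5, 8.1, 8.4 |

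The per-protocol set drops major protocol violators but is supportive only (7.6). Both groups also need a follow-up assessment to be included; that is symmetric and is not the issue. Run-in and DIAN-OBS-only data sit in one reference group (Appendix III), so the reference arm itself mixes two selection rules.

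**2. The plan's own power figure**

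Section 5 gives 95.9% for a 30% effect; Table 15, base case, CPR 0.70, gives 0.959. They agree. The MCMC model cannot be rerun from the document, so I used a normal approximation on the log-CPR scale:

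power = Φ(−ln(CPR)/SE − z), with z = Φ⁻¹(0.981) = 2.075.

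SE is calibrated on the base power of 0.662 at CPR 0.80: SE = 0.2231/(2.075 + 0.418) = 0.0895. This gives 0.873 at CPR 0.75 (Table 15: 0.861) and 0.972 at CPR 0.70 (Table 15: 0.959). It is a consistency check, and the fit worsens at larger effects.

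**3. How much of a DIAN-OBS mismatch reaches the drug effect**

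Scenario H sets all randomized arms to a multiple m of the DIAN-OBS decline. For each H power value P at CPR 0.80:

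shift = SE × (Φ⁻¹(P) + z) − 0.2231; share passed on = −shift/ln(m).

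| m | P | shift | share |
|---|---|---|---|
| 1.2 | 0.171 | −0.122 | 0.67 |
| 1.1 | 0.407 | −0.058 | 0.61 |
| 0.9 | 0.893 | +0.074 | 0.70 |
| 0.8 | 0.981 | +0.148 | 0.66 |

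The CPR 0.75 row gives 0.67, 0.62, 0.63 and 0.61. At CPR 0.70 the values scatter (0.70, 0.74 and 0.32 for m = 1.2, 1.1 and 0.9), because power is near 1 and the constant SE no longer fits. I rely on the first two rows: roughly 60-70%.

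**4. What selection could do, under assumed inputs**

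Let q be the share of DIAN-OBS controls removed and r their decline relative to those kept. Neither is in the SAP; both are assumptions.

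kept/unselected decline = 1/(1 − q + q·r); shift b = 0.66 × ln(that ratio), with positive b favouring the drug; power at CPR 0.70 = Φ((0.3567 + b)/SE − z); type I error = Φ(b/SE − z).

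| q | r | kept/unselected | b | power at CPR 0.70 | true 0.70 reads as | type I error |
|---|---|---|---|---|---|---|
| none | – | 1 | 0 | 0.972 | 0.70 | 0.019 |
| 5% | 1.25 | 0.988 | −0.008 | 0.965 | 0.71 | 0.015 |
| 10% | 1.5 | 0.952 | −0.032 | 0.939 | 0.72 | 0.0075 |
| 20% | 2 | 0.833 | −0.120 | 0.714 | 0.79 | 0.0003 |
| 5% | 0.8 | 1.010 | +0.007 | 0.976 | 0.695 | 0.023 |
| 20% | 0.8 | 1.042 | +0.027 | 0.986 | 0.68 | 0.038 |

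The approximate base type I error of 0.019 exceeds the 0.013 in Table 16, so read the last column for direction and rough scale only.

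**5. Whether the threshold was calibrated against such a mismatch**

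Table 16 lists 13 null scenarios. None lets DIAN-OBS decline differ from the randomized arms; Appendix VI sets such cases aside as not being mathematical nulls. The H block of Table 15 has no CPR 1 row.

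**The case against.** The rule is explicit, pre-specified and given a reason. Several planned analyses limit the harm. Section 12.1.6.2 and items 2 and 3 of 12.1.6.11 drop DIAN-OBS, the MMRM in 12.1.6.9 uses mITT only, and 12.1.6.4 runs from full to no borrowing. The permutation analysis in Appendix VI reassigns treatment among the 140 randomized subjects with DIAN-OBS included, so selected controls should not by themselves produce a small permutation p-value when neither drug works. All of this stands. But these analyses show how far the result depends on DIAN-OBS; every run that uses DIAN-OBS-only controls uses the same selected sample. The permutation result is supportive and changes no threshold.

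Scope is also limited. Run-in data and trial baseline values share the reference group, and Appendix VI suggests that run-in data may make the borrowed sample closer to 120 than 66, which dilutes the effect of removing DIAN-OBS-only subjects.

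A reader might infer that the rule is shown to bias the result, or to favour the drug. The SAP supports neither: bias needs a link between later conditions and decline, and no data on that link are given. If removed subjects decline faster, the error is conservative. A reader might also apply a yearly event rate to the 66 controls in Appendix VI to count losses. No rate is given, and 66 is the number assumed in the simulated analysis, not stated to be a count before exclusions.

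Finally, screening at baseline only and keeping everything afterwards is not automatically right. Protocol Section 4.4.1 is not shown; if it covers such events, that choice would create the opposite asymmetry.

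**Conclusion.** The asymmetry is certain from the text and runs against the stated purpose. The resulting bias is a risk of unknown size and direction. With 5-20% removed and r between 1.25 and 2, approximate power at CPR 0.70 falls from 0.972 to between 0.965 and 0.714. With r = 0.8, approximate type I error rises from 0.019 to 0.023-0.038. These ranges rest on assumed q and r, a 66% pass-through and the normal approximation. The visit-based baseline rule and the look-ahead disqualification can be read together, with the second overriding the first, but they follow different principles and should be reconciled. The rule should be changed because a less bias-prone one is available at little cost; the documents do not show that the primary result would be invalid.

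**What to change.** In Section 7.2, delete the reference to post-baseline visits and the matching loss of all data, and apply Table 3 at the first eligible DIAN-OBS visit. Keep all data up to a later Table 3 event. Handle data after it as the trial handles data after the same event: censor if the event would lead to discontinuation under Protocol Section 4.4.1, otherwise keep. Run the alternative as a sensitivity analysis. Since Section 8.4 states both a cut at discontinuation and a 56-day window, name which one the controls follow. Report how many DIAN-OBS-only controls are affected and how much of their data is involved.

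The cost is a short text change, a rerun of the selection program and one additional model run. Some controls with later comorbidity are retained, as they are in the randomized arms.

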7.3 Demonstration of the Use of the DIAN-OBS Subjects' Data

[Figure 2](#) demonstrates some hypothetical DIAN-OBS subjects. All these subjects are assumed to have CDR between 0 and 1 for at least one visit in the DIAN-OBS. [Table 4](#) represents the application of the eligibility criteria applied to each subject presented in [Figure 2](#).

[figure not shown]

Figure 2: Example DIAN-OBS Subjects Who Would or Would Not Be Eligible to Be Used for Dynamic Borrowing for the Primary Analysis of DIAN-TU-001. Subjects 1 and 2 would not be eligible. Subject 3 would be eligible, but the first data point would not be used. Subjects 4, 5 and 6 would be eligible and all their data points would be used.

Table 4: Application of DIAN-OBS Subject Data Selection as Shown in Figure 2

Subject #	Number of DIAN-OBS Assessments Performed at or after Meeting Eligibility	Eligible for Inclusion as Control?
1	Zero (0) Subject 1 never reached eligibility at a DIAN-OBS visit (did not cross EYO -15 years during their participation)	No. The data from Subject 1 would not be eligible for use as a pooled control.
2	One (1) Subject 2 crossed EYO -15 at their last DIAN-OBS visit	No. The data from Subject 2 would not be used because there is only one visit that occurs after the subject meets EYO eligibility criterion (minimum of 2 required)

Subject #	Number of DIAN-OBS Assessments Performed at or after Meeting Eligibility	Eligible for Inclusion as Control?
3	One (1) Subject 3 crossed EYO -15 at their second DIAN-OBS visit	Yes (partial data). The data from Subject 3's first visit would not be used; however, the data collected at the subsequent visit at which the subject was within -15 EYO would be used.
4	Three (3) Subject 4 met eligibility at their first visit therefore all data collected for this subject would be used.	Yes; All DIAN-OBS data from Subject 4 would be used.
5	Two (2) All visits (2) for this subject occurred at/after the EYO inclusion range	Yes; All DIAN-OBS data from Subject 5 would be used.
6	Five (5) The subject's first visit occurred in the eligible EYO range so all their data may be used	Yes; All DIAN-OBS data from Subject 6 would be used.

In this example, DIAN-OBS Subjects 3 and 5 later enrolled in the DIAN-TU-001 study where one was randomized to the treatment arm and the other to the placebo group. Each of these subjects' data would be included in the primary analysis recognizing them as the same Subject based on their unique subject identifier. For Subject 3, an indicator would be generated to show which data points were collected prior to administration of the active treatment (DIAN-OBS data points + DIAN-TU-001 baseline data point, modeled as controls), and which data points were collected post-administration of the active treatment (modeled as treated).

